3 OBJECTIVES AND ENDPOINTS

OBJECTIVES	ENDPOINTS	JUSTIFICATION FOR ENDPOINTS
Primary		
To evaluate the effectiveness of risk-based messaging and incentives that promote repeated testing for SARS-CoV-2 antibodies	Main effect of incentives, the main effect of messaging strategy, and the interactions between incentives and messaging and covariates; seropositive status	We have found that providing at-risk incentives that can be insured with repeat health behavior outperforms direct cash payments of the same expected value.
Secondary		
To understand social and behavioral determinants of COVID-19 testing and variations within sub-groups of this population.	Characterize barriers to access, bias, risk attitude and incentive preferences through outreach and survey responses. Identify groups that may partition facilitators to testing into minimal and maximal effectiveness.	covariates

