4.1 OVERALL DESIGN

Social determinants need to be understood in the context of actionable facilitators (things COVID-19 policymakers can do) to encourage repeat testing. We will study two types of facilitators (messaging and financial incentives) and evaluate the heterogeneity of treatment response based on the characteristics of those tested. We will conduct a 2 x 2 (messaging x financial incentive) factorial design (Aim 3) that stratifies on social and behavioral determinants (Aim 2) collected as part of an initial survey (Aim 1). We have been studying ways to identify powerful incentives for repeated health behaviors. We have found that providing at-risk incentives that can be insured with repeat health behavior outperforms direct cash payments of the same expected value. Individuals were 70% more likely to return to a health screening when insuring against losing a baseline incentive than they were when paid cash ($p < 0.01$).⁴ In addition, in a recent study we showed that disadvantaged patients at a federally-qualified health center were more likely to repeat a health behavior twice each week over 12 weeks when repetition

was insuring against losing a weekly incentive than if they were paid equivalently in cash (see Figure 1; $p < 0.05$).

5

Figure 1. Insurance (loss protection) vs. cash (control) incentive for repeat health behavior among disadvantaged persons (N = 151)

2 x 2 Stratified Randomization

Messaging (Factor 1): We will develop simple messaging that frames the decision to test in terms of either: (i) family risk, or, (ii) personal risk. These methods will be piloted, but will be of the form "Antibody testing will help you understand your family's risk of getting COVID-19"; and, "Antibody testing will help you understand your risk of getting COVID-19". Family risk framing may engender concern for loved ones. It may also make it easier to mentally simulate family burdens with COVID-19 such as knowing how several people in the family becoming sick could adversely affect the lives of everyone in the family. We hypothesize that the family framing will result in greater uptake of testing and greater repeat testing.

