Incentives (Factor 2): We have been studying incentives for repeat testing since 2015.⁴ We have found that low-income persons respond better to insuring at-risk rewards with repeat behavior than they do to cash payment.⁵ For example, suppose for your first test you are given as an incentive that offers an 80% chance of winning \$52. You then are told you can guarantee winning this lottery by having a second COVID-19 test in 8-months. This is preferable to a \$10 cash payment (i.e., the cost of the insurance against losing an 80:20 bet on \$52) in 8-months. To low-income persons, delivering an attractive lottery incentive for baseline testing and then letting persons insure this lottery with repeat testing may better encourage retesting by giving peace-of-mind and relieving them of worrisome distractions about money that they may already face. We will construct two incentives for this factor: (i) a baseline incentive offering a 90% chance of \$60; (ii) a repeat financial incentive. For (ii) Group 1 receives insurance on winning the baseline incentive; Group 2 receives a lottery incentive offering a 1 in 25 chance of winning \$150. The expected reward for both Group 1 and 2 for having completed both baseline and retest is \$60 (i.e., program costs are the same). In prior work, we've shown that insuring against losing a lottery was more effective than cash payments in the cost of insurance. Here we explore if this also holds true against low-probability and high-reward lotteries for which people may be optimistic about winning.

Messaging and incentives may interact. For example, thinking about the safety of your family after a family-framed message may make insuring against losing a lottery more attractive than another risky lottery.

Testing in a Diverse Population: Sampling low-income populations is important for research on disparities, however, recruiting this population is challenging because they often lack consistent contact information, do not have internet access, and mistrust research. We will use a novel way of recruiting this population by partnering

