9.2 SAMPLE SIZE DETERMINATION

We will recruit a cohort of 2,160 people (540 families), and stratify into 3 subgroups based on predictors of commitment to participation in testing programs. Randomization will be clustered by family. Sub-group membership will be based on the mean household survey response to the survey component. For the purposes of power analyses, we assume high Intra Cluster Correlation within family on uptake of repeat testing (>0.90).

Stratified Allocation Plan and Power Analysis (540 households, 2160 individuals)		
	Control	Intervention
Stratification	# households	# households
HTE Subgroup 1	60	60
HTE Subgroup 2	60	60

HTE Subgroup 3	60	60
% Seropositive in Baseline Test	10%	10%
Total Households Per Arm	180	180
Projected Average Treatment Effect Size	Reference Group	Reference+10%
Minimum Detectable Effect Size Compared to Controls (H4r)	±3%	
Detectable 3-subgroup HTE and Seropositivity (H1r, H2r, H3r)	±7%	

Assuming a similar effect size to prior studies in similar populations, we expect a 10 percentage point difference in repeat testing adherence between intervention and control groups. With 540 households, we are powered to detect as little as 3 percentage point difference between interventions and controls in the 540 households we will enroll. To assess heterogeneity of treatment effects (THE), there is more than 80% power to detect a between-subgroup difference of 7 percentage points, assuming 180 households in each sub-group.

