$$\pi = \beta_0 + \beta_1 x_{ij} + \eta_j + \varepsilon_i \quad [3]$$

For Hypothesis 3r, we will use a simple mixed-effects logistic model, where $\pi = \ln\left(\frac{p}{1-p_i}\right)$, is the probability of Time 2 attendance by individual i in household j given they attended Time 1 testing; β_1 is seropositivity status at Time 1 (yes vs. no); and η_j is the random intercept for each household capturing household-level effects.

We will use two separate models for Hypothesis 4r.

$$\pi = \beta_0 + \beta_1 x_{ij} + \beta_2 x_{ij} + \beta_3 x_{ij} + \beta_4 x_{ij} + \beta_5 x_{ij} + \eta_j + \varepsilon_i \quad [4a]$$

Model 4a will assess the probability, $\pi = \ln\left(\frac{p}{1-p_i}\right)$, of testing attendance for individual i in household j , where β_1 is the main effect for testing time (reference = Time 1); β_2 is the main effect for Financial Incentives (reference = lottery condition); β_3 is the main effect for Messaging (reference = personal); β_4 is the interaction between testing time and Financial Incentives; β_5 is the interaction between testing time and Messaging; and η_j is the random intercept for each household.

$$\pi = \beta_0 + \beta_1 x_{ij} + \beta_2 x_{ij} + \beta_3 x_{ij} + \beta_4 x_{ij} + \beta_5 x_{ij} + \beta_6 x_{ij} + \beta_7 x_{ij} + \eta_j + \varepsilon_i \quad [4b]$$

Model 4b will assess the probability, $\pi = \ln\left(\frac{p}{1-p_i}\right)$, of testing attendance for individual i in household j , where β_1 is the main effect for testing time (reference = Time 1); β_2 through β_4 are the main effects for study arm (personal messaging and loss protection, family messaging and lottery, family messaging and loss protection), where personal messaging and lottery is the reference group; β_5 through β_7 are the interactions between study arm and testing time; and η_j is the random intercept for each household.

For Models 4a and 4b, we will use unrestricted random sampling to select 3,000 observations, 2,000 times, clustered by household to bootstrap 95% confidence intervals for probability differences. We

will test differences in effect sizes for Model 4a (β_4 vs. β_5) and 4b (β_5 vs. β_6 ; β_5 vs. β_7 ; β_6 vs. β_7) using equality of regression coefficients tests.⁶ We will also calculate the inverse of observed probabilities to derive the Number Needed to Intervene on (NNI), and calculate standard errors by taking the square root of $P * (1 - P)/N$.⁷

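### The 10-point effect in section 9.2 is not supported for either contrast the trial tests, and its apparent margin over a 3-point detectable difference does not exist

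*Combined protocol and SAP*

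**What the plan says.** Section 9.2 gives one projected effect: "Assuming a similar effect size to prior studies in similar populations, we expect a 10 percentage point difference in repeat testing adherence between intervention and" the reference arm. The table repeats it as the reference group plus 10%. Neither text nor table names the prior studies, their comparator or their absolute rates. The same section says 540 households can detect a difference as small as 3 points, with an ICC within family above 0.90.

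Section 4.1 describes two prior incentive studies. In the first, "Individuals were 70% more likely to return to a health screening when insuring against losing a baseline incentive than they were when paid cash". The second, in a health-center population, is captioned "Figure 1. Insurance (loss protection) vs. cash (control) incentive for repeat health behavior among disadvantaged persons (N = 151"). Section 3 summarises the evidence the same way: "providing at-risk incentives that can be insured with repeat health behavior outperforms direct cash payments of the same expected value".

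This trial has no cash arm. Everyone is offered a 90% chance of $60 for the first test. For the retest, one group has that prize insured and the other gets a 1 in 25 chance of $150. Section 4.1 presents this as a new question: "Here we explore if this also holds true against low-probability and high-reward lotteries for which people may be optimistic about winning". In Model 4a (section 9.4.1) the incentive coefficient "is the main effect for Financial Incentives (reference = lottery condition"), and the messaging reference is the personal-risk message.

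**The concern.** A projected effect belongs to a comparator. The prior evidence described is against cash, whereas hypothesis 4r is tested against a second lottery and, for messaging, against a second risk message. Section 4.1 treats the lottery comparison as open, so section 9.2 cannot also rely on described prior work for its size. For family v personal framing the documents cite no earlier estimate.

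The sizing looks comfortable because an expected 10 points stands against a detectable 3. If the 3-point figure held, an uncertain projection would do little harm. If it does not, the adequacy of 540 households rests on the 10 points, and its support then matters.

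**Working it through.** **1. Are the two incentives of equal value?** Insurance: $60 certain. Lottery: 0.9 × 60 + 150/25 = 54 + 6 = $60. Yes, so the comparator is an active incentive of the same expected cost.

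**2. Can 10 points be derived from the prior figures?** The only effect size in the text is a 70% relative increase, without absolute rates. The implied difference is 0.7 × cash-arm rate: 7 points at 10%, 21 at 30%, 35 at 50%. It equals 10 points only at 10/0.7 = 14.3%, a rate the documents do not state. Figure 1 is missing from the text available to me and may hold absolute rates, but its caption names cash as the control.

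**3. Does the 3-point detectable difference reproduce?** Inputs from section 9.2: 540 households and 2,160 people (4 per household), ICC above 0.90 (0.90 used, which favours the plan). Assumptions: equal factorial allocation, so 270 households per factor level; two-sided 5%; 80% power (stated only for the subgroup contrast); all enrolled people contribute.

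- Design effect = 1 + 3 × 0.90 = 3.7
- Effective n per level = 270 × 4 / 3.7 = 291.9

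Over reference rates from 1% to 90%, no two-sided detectable difference falls to 3 points; the lowest is 3.9, at a rate of 1%. One-sided, the lowest is 3.3, also at 1%. A two-sided 3.0 does appear if clustering is ignored (n = 1,080 per level) and the reference rate is 5%. The stated figure is not reproduced with the plan's own ICC.

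**4. Power with that ICC.** Power = Φ(d/SE − 1.96) plus a negligible opposite tail, with SE = √{[p0(1−p0) + p1(1−p1)] / 291.9} and p1 = p0 + d. Example, p0 = 0.50 and d = 0.10: SE = √(0.49/291.9) = 0.0410; 0.10/0.0410 = 2.44; power = Φ(0.48) = 0.685.

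The reference retest rate is not stated, so I use a range from the 14.3% of step 2 to 80%.

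| True difference | 14.3% | 30% | 45% | 70% | 80% |
|---|---|---|---|---|---|
| 10 points | 87.0% | 72.1% | 68.0% | 80.2% | 92.7% |
| 7 points | 60.3% | 43.5% | 39.6% | 48.5% | 62.9% |
| 5 points | 36.7% | 25.2% | 22.8% | 27.3% | 35.7% |
| 3 points | 16.9% | 12.2% | 11.2% | 12.7% | 15.4% |
| Detectable at 80% power (points) | 9.0 | 11.0 | 11.5 | 10.0 | 8.4 |

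A pooled-variance test changes the detectable differences by about 0.1 point at most. The section 9.2 table shows 180 households per arm (360 in all, against 540 in the text). With 180 v 180 the effective n is 194.6 and the detectable difference is 10.0 to 14.1 points over the same rates.

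**The case against.** The strongest reply is that several inferences go further than the documents. Each of these stands:

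- A reader might infer that the 10 points *is* an insurance v cash figure. Section 9.2 does not say so. Cash is the comparator in every incentive study described, but the source of the number is unnamed and the number cannot be rebuilt from what is given.
- A reader might infer that the lottery is a stronger comparator than cash, so the true effect must be smaller, perhaps by half. The remark about optimism, and the hypothesis that some people respond to a lottery, do not establish this. The difference could be smaller or larger than against cash.
- A reader might infer that 10 points is explicitly projected for messaging. The projected-effect row carries no hypothesis label; the H4r label sits on the detectable-difference row. The table has a single control and intervention pair and does not say which factor it means.
- A reader might blame the comparator for the low power. The low power comes from applying the ICC: at a true 10 points it is already 68-93%.
- Section 9.4.1 already plans bootstrap 95% intervals for probability differences against named reference conditions, and the cash sentence in section 3 claims no effect size. Neither needs to change for this point.

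The reply fails where it relies on the 3-point figure. The argument that little depends on the 10 points, because the trial can detect 3, requires a detectable difference the stated ICC does not allow.

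**Conclusion.** The point holds in limited form. The documents do not support a 10-point expected effect for insurance v an equal-value lottery or for family v personal messaging. They do not show that 10 points is wrong.

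What is wrong as written is the claim of being powered for 3 points. Under the plan's own ICC the power for 3 points is 11-17%, and the detectable difference is roughly three to four times the stated one (8.4/3 = 2.8 to 11.5/3 = 3.8). A 10-point effect lies inside the range of detectable differences, so it has little margin, and at middling retest rates power for it is below 80%.

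These figures rest on 270 v 270 households, 4 people each, ICC exactly 0.90, a two-sided 5% level and reference rates of 14% to 80%. A higher ICC or fewer contributing households would lower the power. The link from section 9.2 to the cash studies is an inference, so confidence in that part is moderate.

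**What to change.** Change section 9.2 only, text and table:

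1. Stop presenting 10 points as an expected effect carried over from prior studies. Label it a planning value that has not been estimated for insurance v lottery or for family v personal messaging. Describe it as an insurance v cash figure only if the sponsor confirms that source.
2. Replace the claim of being powered for 3 points with household-level power at 3, 5, 7 and 10 points. Give this for each factor contrast, with the stated ICC, the alpha level and sidedness, and a stated range of reference retest rates.

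This adds no participants and leaves the allocation and models alone. The cost is a less favourable sizing statement.

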9.1 STATISTICAL HYPOTHESES

The figure below provides a conceptual diagram for thinking about what factors may influence testing take-up and retesting. Testing take-up would depend on several factors, including prior beliefs about infection, health literacy, information networks, health conditions, demographics and socio-economics. We have the following hypothesis based on analysis of literature on testing for HIV and Hepatitis as well as preliminary analysis of data from our prior study:

Hypothesis 1: Those who believe that they have been infected in the past would be more likely agree to testing to confirm that they have antibodies and potential immunity; **Hypothesis 2:** People with poor health literacy will be less likely to agree to testing as they might find it daunting to understand what the test does and how to interpret results; **Hypothesis 3:** Those who are risk averse would be more likely to agree to testing as it reduces uncertainty about serostatus; **Hypothesis 4:** Those with preexisting health conditions would be more likely to agree to testing as they face higher risks from COVID-19 and thus have more to gain from learning serostatus; **Hypothesis 5:** Minorities and those in lower socio-

economic strata would be less likely to agree to testing due to fear of discrimination, lack of trust in health care/research, poor past experience, and perception of being at low risk of infection. We also generate hypotheses for facilitators to retesting (r) relative to those who take a first test **Hypothesis 1r:** Persons who practice low COVID-19 mitigation, exhibit risk-seeking and have high exposure risk may respond to a lottery retest incentive. **Hypothesis 2r:** Those persons with low income, unemployed, or have high stress or anxiety may respond most to insurance of incentives. **Hypothesis 3r:** Persons who are sero+ at baseline will be less likely to return for a retest. **Hypothesis 4r:** Lottery insurance and family messaging will induce higher retesting rates. Hypotheses 1-5 are covariates that may affect agreeing to the test. Hypotheses 1r and 2r refer to heterogeneity of treatment effects for retesting, while 3r and 4r are main effects on retesting.

Conceptual diagram

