9.4 STATISTICAL ANALYSES

9.4.1 GENERAL APPROACH

Aim 1 (Hypotheses 1-5): Data from the baseline survey combined with data on which heads of households attended Time 1 testing will be used to address Aim 1. In particular, we will estimate logistic regressions where the dependent variable will be the binary indicator whether the head of household attended Time 1 testing (yes vs. no). The key independent variables will include: 1) prior COVID-19 testing, 2) which SARS-CoV-2 information sources are most trusted, 3) risk aversion, 4) heads of households or family member diagnosis of a health condition (e.g., diabetes, hypertension) and, 5) race/ethnicity, income, discriminatory incidences, household receipt of Supplemental Nutrition Assistance Program (SNAP) or Supplemental Security Income (SSI) benefits, and citing money as the biggest vaccine barrier.

$$\pi = \beta_0 + \beta_1 x_i + \varepsilon_i \quad [1]$$

$\pi = \ln\left(\frac{p}{1-p_i}\right)$; p_i , is the probability of attending Time 1 testing, by head of household i , and β_1 is each head of household reported social determinant of health. This will allow us to identify significant social and behavioral determinants for heterogeneity of effects (currently hypothesized in Hypotheses 1-5 above).

Aim 2 (Hypotheses 1r-4r): Aim 2 will involve regressing Time 2 retesting (yes vs. no) on the following items for Hypotheses 1r-4r: 1r) risk aversion, essential worker status, access to personal protective equipment, and risky forms of transportation (e.g., personal vehicle, carpool, bus), 2r) income, discriminatory incidences, employment status, whether heads of households personally, or other family members suffer from depression and/or mental health issues, and household receipt of Supplemental Nutrition Assistance Program (SNAP) or Supplemental Security Income (SSI) benefits, 3r) Time 1 seropositivity status and, 4r) the Financial Incentive and Messaging study arms.

$$\pi = \beta_0 + \beta_1 x_i + \beta_2 x_i + \beta_3 x_i + \varepsilon_i \quad [2]$$

For Hypotheses 1r-2r, $\pi = \ln\left(\frac{p}{1-p_i}\right)$, is the probability of Time 2 attendance by head of household i given they attended Time 1 testing; β_1 is the main effect of the head of household reported characteristic, β_2 is the main effect of the Financial Incentive, where the lottery condition is the reference, and β_3 is the interaction between the head of household reported social determinant of health and Financial Incentive.

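### The 3-point detectable difference for H4r in Section 9.2 is not reached for the Time 2 retest contrast at the plan's own ICC, and the 7-point HTE figure needs its contrast defined

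*Combined protocol and SAP*

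**What the plan says.** Section 9.2 plans 2,160 people in 540 families. It states that "Randomization will be clustered by family" and that, for power, "we assume high Intra Cluster Correlation within family on uptake of repeat testing (>0.90". It gives three effect sizes:

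- **Projected effect:** "we expect a 10 percentage point difference in repeat testing adherence between intervention and control groups".
- **Main comparison (H4r):** "we are powered to detect as little as 3 percentage point difference between interventions and controls in the 540 households we will enroll".
- **Heterogeneity:** "there is more than 80% power to detect a between-subgroup difference of 7 percentage points, assuming 180 households in each sub-group". The table row for this figure is labelled HTE and seropositivity, and covers H1r, H2r and H3r.

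Section 9.1 says "Hypotheses 1r and 2r refer to heterogeneity of treatment effects for retesting". In Section 9.4.1, the third coefficient of Model 2 "is the interaction between the head of household reported social determinant of health and Financial Incentive", and the modelled quantity "is the probability of Time 2 attendance by head of household i given they attended Time 1 testing". H4r is tested in Models 4a and 4b through interactions of testing time with factor or arm, with one random intercept per household.

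Section 9.2 states no reference retest rate, no alpha, no power for the 3-point figure and no Time 1–Time 2 correlation. Its table shows a Control and an Intervention column, although the design is a 2x2 factorial.

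**The concern.** At an ICC of 0.90 or more, four members of one household carry little more information than one. The trial then has roughly one independent observation per household, and the largest factor-level contrast in the 2x2 is 270 v 270 households. A 3-point detectable difference looks too small for that.

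At stake is the stated power for the hypothesis that serves the primary objective. A 3-point limit makes the projected 10-point effect look more than three times what the trial can detect (10/3 = 3.3). If the real limit is 8 to 11.5 points, the projected effect lies close to it. The 7-point figure raises the same question for heterogeneity, because an interaction needs far more information than a comparison of two rates.

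**Working it through.** **Inputs from the plan.** 540 households and 2,160 people, so 4 per household; clustered randomization; ICC 0.90, the lower bound, which is the most favourable value for a single-time contrast. **Assumed.** Two-sided 5%, 80% power, equal allocation, equal household size, no loss. The reference rate is not given, so a range is shown. The table's Reference+10% row caps it at 90%.

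**1. The 3-point figure, Time 2 contrast.**

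Design effect = 1 + (4 − 1) × 0.90 = 3.7. Effective total = 2,160/3.7 = 583.8. Effective n per factor level = 1,080/3.7 = 291.9.

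Power = Φ{[Δ − 1.96√(2p̄(1−p̄)/n)] / √([p₁(1−p₁) + p₂(1−p₂)]/n)}, plus the small opposite tail.

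At p₁ = 0.50 and Δ = 0.03, the null SE is √(2 × 0.2498/291.9) = 0.0414 and the alternative SE is 0.0413. Then (0.03 − 0.0811)/0.0413 ≈ −1.24, and power is 0.112 with both tails. Solving for 80% power:

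| Reference rate | Detectable, ICC 0.90 (points) | Detectable, ICC 1.0 | Detectable, clustering ignored | Power for 3 points, ICC 0.90 | Households needed for 3 points |
|---|---|---|---|---|---|
| 10% | 8.0 | 8.4 | 3.9 | 0.206 | about 3,280 |
| 50% | 11.5 | 11.9 | 6.0 | 0.112 | about 8,060 |
| 80% | 8.4 | 8.7 | 4.6 | 0.154 | about 4,860 |
| 90% | 5.9 | 6.1 | 3.3 | 0.255 | about 2,510 |

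Even at a 1% rate the detectable difference is 3.9 points. So 3 points is not reproduced at any rate from 1% to 90%. Ignoring clustering does not rescue it at 10% to 90%.

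**2. The projected 10 points, same contrast.** Factor-level power is 0.925 at 10%, 0.677 at 45% and 0.925 at 80%. It is below 0.80 between about 20% and 70%. For one arm against the reference arm (135 v 135 households, n = 540/3.7 = 145.9), the detectable difference is 12.0 points at 10%, 16.1 at 50% and 11.4 at 80%. Power for 10 points is 0.40 to 0.67 over 10% to 80%.

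**3. Time-by-arm terms (Models 4a/4b), linear approximation with equal rates at both times.** Let r be the correlation between a Time 1 and a Time 2 observation in one household. The variance of a household mean at one time is p(1−p) × 3.7/4 = 0.925p(1−p). The SE of the difference in change is √(4p(1−p)(0.925 − r)/270), and the detectable difference is 2.80 × SE.

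| r | At p = 10% | At p = 50% |
|---|---|---|
| 0.90 | 1.6 | 2.7 |
| 0.50 | 6.7 | 11.1 |
| 0 | 9.8 | 16.4 |

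Setting the result to 3 points gives (0.03/2.80)² × 270/4 = 0.00775. Hence r = 0.925 − 0.00775/0.09 = 0.84 at 10%, and 0.925 − 0.00775/0.25 = 0.89 at 50%.

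**4. The 7-point figure.**

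*As a difference in treatment effects:* SE = √(4p(1−p)/n), with n per cell.

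- Two 180-household subgroups, all members: n = 90 × 4/3.7 = 97.3. Power for 7 points is 0.106 at 50% and 0.210 at 10% or 90%.
- Same subgroups, one head per household: n = 90. Power is 0.102 to 0.198; the detectable interaction is 17.7 to 29.5 points.
- Evenly split covariate over all 540 heads: n = 540/4 = 135. Power is 0.129 to 0.273; the detectable interaction is 14.5 to 24.1 points.

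*As a plain difference in rates*, 180 v 180 households (n = 720/3.7 = 194.6): power is 0.524 at 10%, 0.282 at 50%, 0.460 at 80% and 0.802 at 90%. It reaches 0.80 only at rates of about 3% or below, or 90% or above.

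**The case against.** The strongest objection is that the two-proportion calculation is not the planned H4r test. Models 4a and 4b estimate a change from Time 1 to Time 2 with one household intercept across both times. If the 0.90 correlation spans all eight household observations, 3 points is attainable (step 3), and a higher ICC then helps. This stands in part. A reader might take 8 to 11.5 points as the value for Model 4a; the documents do not support that, since the true figure could be lower or higher. But Section 9.2 ties its ICC to uptake of repeat testing and says nothing about correlation between times. Even with a shared 0.90, simulated power for 3 points (270 v 270, rates 10% to 80%) was 78% to 97% when individuals change status, but 58% to 77% when whole households do. If everyone attends Time 1, the gain disappears.

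The 7-point sentence can be read as a plain difference between subgroups, and its row also covers H3r, a main effect. That stands: the shortfall against the claimed 80% is as large as stated only on the heterogeneity reading. That reading has support in the row label, Section 9.1 and Model 2. H3r is not challenged here. The weight of heterogeneity also varies: Section 3 lists covariate interactions under the primary objective, while the synopsis lists heterogeneous effects as secondary and Section 9.4.2 treats them as exploratory.

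A reader might also infer that a null result would be taken to exclude effects above 3 points. The documents do not support this: Section 9.4.1 plans bootstrap 95% confidence intervals for probability differences, which will show the precision achieved.

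**Conclusion.** The concern holds for the contrast that Section 9.2 describes. With its own clustering and ICC, 270 v 270 households detect about 5.9 to 11.5 points at reference rates of 10% to 90%, not 3, and power for 3 points is about 11% to 25%. For the time-by-arm terms, 3 points is reached only if a correlation near 0.90 carries across both times, which the plan does not state. The 7-point figure fails widely as a difference in treatment effects, and holds only at extreme rates as a plain difference.

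These values rest on the assumptions listed in the working. For the Time 2 contrast, loss, unequal household sizes or a higher ICC would make them worse. With no stated reference rate there is no single correct replacement. It would be too strong to conclude that the trial cannot detect its projected effect: factor-level power for 10 points is about 93% at reference rates of 10% or 80%, and falls to about 68% near 45%.

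**What to change.** In Section 9.2, with no change in enrolment or models:

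1. State the reference retest rate, alpha, power, ICC and assumed Time 1–Time 2 correlation.
2. Withdraw the 3-point figure. Restate the detectable difference for the Time 2 retest contrast: roughly 8 to 11.5 points at factor level and 11 to 16 for one arm against the reference arm, at rates of 10% to 80%. Compute the Model 4a and 4b time-by-arm values separately under the stated correlation.
3. Say which contrast the 7-point figure means. For H1r and H2r, restate it as an interaction in heads of household who attended Time 1: about 14 to 24 points with an evenly split covariate over all 540 heads, or about 18 to 30 between two 180-household subgroups, before loss.
4. Reconcile the Control/Intervention table with the 2x2 design. Three strata by four cells gives 540/12 = 45 households per cell if allocation is equal.

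The cost is protocol wording and a short recalculation. The downside is less favourable stated figures.
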